### **2.3. Benefit/Risk Assessment**

Currently available approaches to presbyopia correction include nonsurgical options (spectacles or contact lenses) and surgical options (PRK or LASIK, conductive keratoplasty, intraocular lenses, or corneal inlays). Each approach has its own risk-benefit ratio. Because the risk-benefit ratio with nonsurgical options is generally lower than that of surgical procedures, both historical and contemporary practice has been to attempt nonsurgical or pharmacological treatment before resorting to more invasive alternatives.

Although the use of spectacles and contact lenses to correct presbyopia is widespread, this approach has limitations. Multifocal spectacles impair depth perception and edge-contrast sensitivity at critical distances for detecting obstacles in the environment ([Lord 2002](#)), and varifocal lenses have a corridor of nondistorted vision. For these reasons, older people are more than twice as likely to fall when wearing multifocal spectacles, and many participants have difficulty adjusting to using them ([Johnson 2007](#), [Lord 2002](#)). As a result, the sponsor is developing a noninvasive, reversible, pharmacological treatment for presbyopia.

Considering the COVID-19 pandemic, the benefit and risk to participants in this study have been re-evaluated. Based on the limited information to date, no additional risk to study participants is anticipated with the use of AGN-190584 and no potential interactions are anticipated between the COVID-19 vaccine and the study drug.

More detailed information about the known and expected benefits and risks and reasonably expected AEs of AGN-190584 may be found in the IB.

### 3. Objectives and Measures

Objectives	Measures
To evaluate night-driving performance in real-world driving conditions in participants with presbyopia treated with AGN-190584 versus vehicle	
 
• Overall driving performance
 
• Hazard avoidance
 
• Road sign recognition
 
• Road sign recognition distance
 
• Pedestrian recognition distance
 
• Lane-keeping
 
• Driving time
 
• Pupil diameter
 
• Halometer
 
• Night driving experience questionnaire
 

To evaluate safety in participants with presbyopia treated with AGN-190584 versus vehicle	
 
• Mesopic/photopic HDVA
 
• AEs
 
• Pregnancy tests for WOCBP
 
• Slit-lamp biomicroscopy
 

## **4. Study Design**

### **4.1. Overall Design**

This is a single-center, randomized, double-masked, crossover, Phase 3b study evaluating the effect of AGN-190584 compared with vehicle when dosed in both eyes on driving performance under real-world, night-lighting conditions in participants with objective and subjective evidence of presbyopia.

The study consists of 5 visits (screening [Visit 1], randomization/first dosing [Visit 2], first driving [Visit 3], second dosing [Visit 4], and second driving [Visit 5] visits) with a crossover of AGN-190584 and vehicle. There will be a 7- to 14-day study intervention adaptation period before each driving visit (Visits 3 and 5) and a 7- to 42-day washout period between Visits 3 and 4. Participants will require transport to and from both of the driving visits.

Approximately 54 participants will be enrolled at one study site (Queensland University of Technology, Australia) and approximately 40 participants are expected to complete the study based on an anticipated dropout rate of 25% or less. Participants who prematurely discontinue from the study will not be replaced.

### **4.2. Scientific Rationale for Study Design**

The current Phase 3b clinical study is designed to evaluate the effect of AGN-190584 compared with vehicle when dosed in both eyes on driving performance under real-world, night-lighting conditions in participants with presbyopia.

Phase 2 Studies 199201-009 and 199201-010 supported the administration of AGN-190584 monotherapy as an effective and safe treatment for presbyopia at doses up to 1.5%. The nearly completed Phase 3 Studies 1883-301-013 and 1883-302-013 evaluated AGN-190584 1.25% in an expanded participant population to establish efficacy and safety (data analysis and CSRs in progress).

As with all miotics, participants should be advised to exercise caution in night driving and other hazardous occupations in poor illumination. Participants should be advised not to drive or use machinery until vision is cleared. This study is being conducted to better understand and quantify the effect of AGN-190584 on night driving under real-world conditions.

### **4.3. Justification for Dose**

Through modeling and evaluation of the Phase 2 results (Studies 199201-007, 199201-009, and 199201-010), the sponsor has determined the optimal dose of AGN-190584 to be 1.25% for the treatment of presbyopia. AGN-190584 1.25% was evaluated in 2 nearly completed Phase 3 studies (1883-301-013 and 1883-302-013). The analyses and CSRs for these studies have been completed.

#### **4.4. End of Study Definition**

The EOS is defined as the date of the last driving visit of the last participant in the study.

A participant is considered to have completed the study if he/she has completed all phases of the study including the last driving visit.

## 5. Study Population

The study population will consist of adult male and female participants with objective and subjective evidence of presbyopia.

Prospective approval of protocol deviations to recruitment and enrollment criteria, also known as protocol waivers or exemptions, is not permitted.

### 5.1. Inclusion Criteria

Participants are eligible to be included in the study only if all of the following criteria apply:

1.	Age
1.01	Participant must be 40 to 55 years of age inclusive, at the time of the screening visit.
2.	Type of Participant and Presbyopia Characteristics
2.01	In good general health at the screening visit, as determined by the investigator from medical history
2.02	Subjective complaints of poor near vision that impacts activities of daily living, as defined by at least a moderate impact (score $\geq 3$ ) on at least 1 question on NEI VFQ-25 Questions 5 to 7 in the main questionnaire or near vision subscale, Questions A3 to A5 in the Appendix of Optional Additional Questions, at the screening visit  Note: Please advise the participant that for this questionnaire they are to interpret the instructions as referring to glasses or contacts they need for seeing objects at a distance (if required), not their reading glasses or bifocals.
2.03	Photopic, high-contrast, best distance correction in the range of spherical -4.00 D to +1.00 D inclusively and cylinder $\leq \pm 2.00$ D with photopic at the screening visit and photopic, high-contrast BCDVA of 20/25 or better OD and OS at the screening visit
2.04	Photopic, high-contrast HDVA of 20/32 or better OU at screening as well as before and 1 hour after dosing at both driving tests. Only monofocal correction (either spectacles or contact lenses) is allowed for the driving tests. If the participant does not have monofocal correction of 20/32 or better OU, the study site will provide monofocal spectacles.
2.05	Mesopic, high-contrast DCNVA of 20/40 to 20/100 OD and OS at screening
2.06	Photopic, high-contrast near visual acuity correctable to 20/40 or better in each eye at the screening visit
2.07	Mesopic pupil diameter $< 8.0$ mm in both eyes at the screening visit

3.	Sex
3.01	Male or female
4.	Informed Consent
4.01	Capable of giving signed informed consent, which includes compliance with the requirements and restrictions listed in the ICF and in this protocol
4.02	Written informed consent from the participant or a legally authorized representative has been obtained prior to any study-related procedures.
4.03	Written documentation has been obtained in accordance with the relevant country and local privacy requirements, where applicable.
5.	Other
5.01	Participant must hold a valid driver's license as governed by local regulations.
5.02	Able, as assessed by the investigator, and willing to follow study instructions and likely to complete all required study visits

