			Before Dosing	After Dosing			Before Dosing	After Dosing	Before dosing (before study intervention instillation) and after dosing (approximately 1 hour after study intervention instillation)
Photopic manifest refraction (distance and near)	X								Please see Section 8.2.1.2.
Mesopic conditions: allow for dark adaptation (5 to 10 minutes in mesopic conditions). Perform under mesopic conditions (3.2 to 3.5 cd/m  ; 10 to 11 lux at target).			X	X			X	X	Carry out in the order specified.
Mesopic, high-contrast, binocular HDVA			X	X			X	X	At the driving visits, measurement is conducted with habitual correction for OU only.
Mesopic pupil diameter			X	X			X	X	Please see Section 8.1.7.
Halometer			X				X		Please see Section 8.1.8.

Procedures	Study Days (Visits)							Notes	
	Screening (Visit 1)	Randomization/ First Dosing Visit (Visit 2)	First Driving Visit (Visit 3)		Washout Period	Second Dosing Visit (Visit 4)	Second Driving Visit/ Early Exit (Visit 5)		
Visit Windows	Days -30 to -1	Day 1 (to be scheduled between 08:00 and 10:00)	Days 8 to 15		7 to 42 days	Days 15 to 57 (to be scheduled between 08:00 and 10:00)	Days 22 to 71		7- to 14-day study intervention adaptation period between Visits 2/3 and 4/5
			Before Dosing	After Dosing			Before Dosing	After Dosing	Before dosing (before study intervention instillation) and after dosing (approximately 1 hour after study intervention instillation)
Photopic conditions: perform under photopic conditions ( $\geq 80$ cd/m  ; 251 lux at target).			X	X			X	X	
Photopic, high contrast, binocular HDVA			X	X			X	X	Measurement is conducted OU only with habitual correction.
Photopic pupil diameter			X	X			X	X	Please see Section 8.1.7.
Fluorescein corneal stain	X								Please see Section 0, Item 4.02 (exclusion criteria).
IOP measurement	X	X				X			Please see Section 0, Item 4.07 (exclusion criteria).
Gonioscopy/angle assessment	X								Please see Section 0, Item 4.04 (exclusion criteria).
Dilated fundoscopic examination	X								Please see Section 8.2.1.3.
Review inclusion and exclusion criteria	X	X							Please see Section 5.1 and Section 0 (inclusion and exclusion criteria).

Procedures	Study Days (Visits)							Notes	
	Screening (Visit 1)	Randomization/ First Dosing Visit (Visit 2)	First Driving Visit (Visit 3)		Washout Period	Second Dosing Visit (Visit 4)	Second Driving Visit/ Early Exit (Visit 5)		

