### **5.3. Lifestyle Considerations**

Participants who wear bifocal or multifocal spectacles or contact lenses will be provided a pair of monofocal spectacles with the same or improved distance correction (20/32 or better) as their new habitual correction for use at the driving visits. Bifocal or multifocal spectacles or contact lenses for habitual correction are permissible throughout the study, although they cannot be used at the driving visits.

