### **7.1. Discontinuation of Study Intervention**

See the SoA (Section 1.3) for data to be collected at the time of early exit.

Participants who discontinue the study intervention early will be encouraged to stay in the study for the safety assessments at the second driving visit.

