### 8.1. Efficacy Assessments – Driving Performance

Efficacy assessments for night-driving performance metrics include: sign recognition (Section 8.1.1), hazard avoidance (Section 8.1.2), driving time (Section 8.1.3), lane-keeping (Section 8.1.4), pedestrian recognition distance (Section 8.1.5), overall composite driving Z-score (Section 8.1.6), pupil diameter (Section 8.1.7), halometer (Section 8.1.8), and a night-driving experience questionnaire (Section 8.1.9).

The night-driving evaluation will be performed at both driving visits. Please see the SoA in Section 1.3 for the timing of events at each visit.

Pupil diameter and halometer measurements will be performed separately from the driving test. Please see the SoA in Section 1.3 for the timing of events at each visit.

After 1 hour  $\pm$  15 minutes following study intervention instillation and visual function assessments, participants will start the driving test at the beginning of the closed road driving circuit. The circuit is representative of a rural road, and includes hills, bends, curves, intersections, lengthy straight sections, and standard road signs and lane markings. The circuit does not include artificial ambient lighting. All experimental sessions will be conducted during times when the road surface is dry and there is no rain. Driving performance will be assessed after nautical twilight (evening nautical twilight is defined to begin at sunset and end when the center of the sun is 12 degrees below the horizon).

Participants will undergo a 5-minute familiarization period with the instrumented vehicle and provided with standard instructions regarding the driving circuit and the tasks.

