**8.2.5. Mesopic and Photopic HDVA**

Binocular HDVA will be tested using logMAR charts at 4 m under 2 lighting conditions: mesopic luminance (10 to 11 lux) and photopic luminance ( $\geq 251$  lux) under normal room lighting. Testing will be conducted with the participant's habitual monovision distance refractive correction. Forced choice letter-by-letter scoring will be used for each test and the total number of correct letters or the highest value (number) of the grid identified (as applicable) will be recorded, in logMAR. Different logMAR charts will be used for each lighting condition and distance measured.

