### 9.2. Sample Size Determination

The sample size calculation is based on the primary efficacy endpoint. Assuming no difference between treatment groups and variance of 0.11, approximately 40 participants will be required to obtain 90% power for a 1-sided noninferiority test with type 1 error of 0.025 and noninferiority margin of -0.25 units in mean overall composite driving Z score. Therefore, approximately 54 participants will be enrolled to achieve 40 participants completing the study assuming an anticipated dropout rate of 25% or less.

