5.0 Subject Disposition

The total number of participants who were screened, enrolled (randomized), and treated will be summarized. Reasons for exclusion, including screen failure, will be summarized.

A summary of participant accountability will be provided where the number of participants in each of the following categories will be summarized for each intervention group:

- participants randomized in the study;
- participants who took at least one dose of study drug;

- participants who completed protocol-specified treatment;
- participants who prematurely discontinued study drug and reasons for discontinuation;
- participants in each analysis population, as applicable.

Participant disposition will be summarized by study intervention sequence for the entire study and for Period 1 and Period 2.

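### The post-dose acuity clause of inclusion 2.04 does not fit the drive instructions, and no prespecified analysis tests noninferiority against missing AGN-190584 drives that are worse than MAR predicts

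*Protocol*

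**What the plan says.** **The acuity clause.** Protocol 5.1, criterion 2.04, requires "Photopic, high-contrast HDVA of 20/32 or better OU at screening as well as before and 1 hour after dosing at both driving tests". It adds that the site supplies monofocal spectacles to anyone whose monofocal correction does not reach 20/32. Section 5.3 gives bifocal and multifocal wearers such spectacles "as their new habitual correction for use at the driving visits". In Table 1-1 the row "Review inclusion and exclusion criteria" is marked at Visits 1 and 2 only. Photopic HDVA is measured before and after dosing at Visits 3 and 5, with no consequence attached. Under Protocol 8.1, once the post-instillation interval and the visual function assessments are over, "participants will start the driving test at the beginning of the closed road driving circuit".

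**Stopping early.** Protocol 9.2 enrols about 54 to have 40 complete, "assuming an anticipated dropout rate of 25% or less". Section 4.1 rules out replacement. Section 7 lists adverse event among the reasons for ending treatment. Section 7.1 refers to the schedule for early-exit data and says that participants who stop study intervention are "encouraged to stay in the study for the safety assessments at the second driving visit". In Table 1-1 the Visit 5 column is also the early-exit column, and the driving test is marked in it.

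**Analysis.** Efficacy is analysed in all randomized participants (SAP 8.1). Missing primary-endpoint data are handled by the MMRM under MAR (SAP 8.3.2). SAP 8.3.4 adds descriptive statistics on observed data, without imputation. SAP 5.0 reports "participants who prematurely discontinued study drug and reasons for discontinuation", with disposition by sequence overall and in each period.

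**The acuity measurement.** Protocol 8.2.5 tests HDVA with the "habitual monovision distance refractive correction", and Table 1-1 also specifies habitual correction. SAP 9.5.2 says that the test uses optimal correction.

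**The concern.** An eligibility criterion that refers to a measurement taken after randomization, and at one of the two drives on active drug, invites two readings. On one, the drive goes ahead whatever the acuity. On the other, a participant below 20/32 does not drive. On the second reading the drives most likely to be lost are those on AGN-190584 in participants whose vision it affects most.

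The second route to missing drives does not depend on 2.04. Participants may stop treatment for visual adverse events. SAP Appendix B names blurred vision, reduced acuity, glare and halo vision among its terms of special interest. The text does not settle whether those participants still drive.

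By either route, if the missing AGN-190584 drives would have been worse than MAR predicts, the estimated difference moves toward noninferiority. That is the favourable conclusion on a road-safety question, and the plan contains no prespecified analysis that would show whether it survives.

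**Working it through.** **1. The plan's own figure.** The inputs are in Protocol 9.2 and SAP 2.4: true difference 0, variance 0.11, margin -0.25, one-sided 0.025, 90% power. The type of variance is not stated. Taking 0.11 as within-participant variance, the variance of a paired difference is 2 × 0.11 = 0.22 (SD 0.47).

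- Normal approximation: N = 0.22 × (1.96 + 1.28)² / 0.25² = 37.0.
- Noncentral t with N - 2 df: N = 40, power 90.7%.
- Dropout: 40 / 0.75 = 53.3, so 54.

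The plan's 40 and 54 are reproduced. Taking 0.11 as the variance of the paired difference would give 21, so the within-participant reading is used below.

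**2. False noninferiority.** Let k AGN-190584 drives be lost from participants whose true difference is D, and let the other non-completers resemble the rest. Both k and D are assumptions; the documents give neither. Set the all-randomized difference at -0.25, where the error rate should be 2.5%. The effect among the others is

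(-0.25 - (k/54) × D) / (1 - k/54),

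tested on 40 pairs with SE = √(0.22/40) = 0.0742 and 38 df.

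| k | D | Effect among the others | P(noninferiority declared) |
|---|---|---|---|
| 4 or 7 | -0.25 | -0.250 | 2.5% |
| 4 | -0.5 | -0.230 | 4.5% |
| 4 | -0.75 | -0.210 | 7.6% |
| 4 | -1.0 | -0.190 | 12.1% |
| 7 | -0.5 | -0.213 | 7.1% |
| 7 | -0.75 | -0.176 | 16.3% |
| 7 | -1.0 | -0.138 | 31.1% |

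Here k = 7 is half of the 14 non-completers that the plan allows (54 - 40). A likelihood-based crossover simulation that keeps the vehicle drives of these participants (1,500 runs, intraclass correlation 0.67 assumed) gives 3.9% and 10.7% for k = 4, and 6.5% and 29.8% for k = 7, at D = -0.5 and -1.0. Keeping those vehicle drives therefore removes little of the inflation.

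**3. Tipping shift.** This is how much worse than their MAR prediction the missing AGN-190584 drives must be for the lower bound to reach -0.25. At an observed difference of 0 the half-width is 2.024 × 0.0742 = 0.150, which leaves 0.250 - 0.150 = 0.100. With p = k/54:

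- SE held fixed: shift = 0.100 / p.
- SE including the variance that the shift adds (an approximation): solve p × s + 2.024 × √(0.22/40 + p(1 - p)s²/54) = 0.25 for s.

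| k | SE fixed | With added variance |
|---|---|---|
| 4 | 1.35 | 1.09 |
| 7 | 0.77 | 0.67 |
| 14 | 0.39 | 0.36 |

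Divided by the SD of a paired difference (0.47), the fixed-SE shifts are 2.9, 1.6 and 0.8. If the observed difference were -0.05, they would be 0.67, 0.39 and 0.19 Z units.

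**The case against.** Three stronger readings are tempting, and the documents do not support them.

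*That 2.04 removes drives and so biases the result.* No passage says that a failed post-dose check bars the drive. Protocol 8.1 with the ITT rule points to holding and analysing it, and then there is no bias. The spectacles provision is also consistent with a requirement on the correction worn for the drive. Selective loss through 2.04 is a possibility created by unclear wording.

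*That participants who stop treatment do not drive.* Section 7.1 names only safety assessments, but it also points to the schedule, whose early-exit column includes the driving test. The position is unclear; the protocol does not exclude the drive.

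*That nothing would show why drives are missing.* Sequence by period identifies treatment, so the disposition output in SAP 5.0 goes a long way. Reasons for discontinuation are on the eCRF (Protocol 7), and adverse events leading to discontinuation are tabulated and listed (SAP 9.2.4). HDVA is summarized by treatment with minimum and maximum (SAP 9.1 and 9.5.2). The remaining gaps are the reason for a drive missed without discontinuation and a count of post-dose acuity worse than 20/32.

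On size, the 25% is an all-cause ceiling, and Section 7 also lists COVID-19 and loss to follow-up. Protocol 2.2 calls Phase 2 discontinuation generally low and most adverse events mild to moderate. D = -1.0 is four times the margin. MAR is a stated and common primary assumption, and a reader could approximate the tipping shift from the reported interval and n. These points limit the severity. They do not replace a prespecified check: the compound-symmetry fallback deals with convergence only, and SAP 8.3.4 is descriptive.

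**Conclusion.** The point holds as a cheap improvement to the plan. It does not show that the primary analysis is wrong. Criterion 2.04, Table 1-1 and Section 8.1 need reconciling, as do Section 7.1 and the early-exit column, and the HDVA correction in SAP 9.5.2 contradicts the protocol. The HDVA conflict does not touch the primary endpoint.

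The noninferiority conclusion rests on MAR alone. With 4 lost AGN-190584 drives the assumed scenarios give 4.5% to 12.1% false noninferiority, and with 7 they give 7.1% to 31.1%, against 2.5% nominal. There is no inflation if the lost drives resemble the rest. At an observed difference of 0, a few lost drives would have to be implausibly poor to overturn the result (more than 1 Z unit below prediction for 4). If all 14 permitted non-completers lacked the AGN-190584 drive, about 0.36 to 0.39 Z units would be enough. The higher figures are upper scenarios. All of them assume that 0.11 is within-participant variance and that exactly 40 pairs are available.

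**What to change.** (a) Reconcile the post-dose clause and spectacles sentence of 2.04 with Table 1-1 and Sections 5.3 and 8.1; Section 7.1 with the early-exit column; and the HDVA correction in SAP 9.5.2 with Table 1-1 and Protocol 8.2.5. What any post-dose rule should say is for the sponsor; none is proposed here.

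(b) Extend the disposition output to missing drives by treatment and period with the reason, including drives missed without discontinuation. Count post-dose HDVA worse than 20/32 by treatment.

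(c) Keep the MMRM under MAR as the primary analysis. Before unmasking, add to SAP 8.3.4 a delta-adjusted tipping-point analysis by multiple imputation. Impute missing drives under MAR, then shift only the missing AGN-190584 drives down in steps until the lower 95% bound reaches -0.25. State how participants with neither drive are handled, and report the shift.

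The cost is one wording reconciliation, two small tabulations (with an eCRF field for the reason if it is not already captured) and one sensitivity analysis, whose result may be less favourable. The sample size, primary analysis and power (about 91% with 40) do not change.
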